2.4. ESTIMANDS

The primary estimand is the difference in effect for galcanezumab compared to rimegepant in participants with episodic migraine on the overall mean monthly 50% response rate (defined as participants with at least a 50% reduction from baseline in the frequency of migraine headache days) across the 3-month double-blind period (See estimand in Table E below).

All available monthly migraine headache data will contribute to analysis as long as baseline monthly migraine headache day values are available. Any migraine headache day after study

Document: **CCI**

Author: **PPD**

Version Number:

3.0

Version Date:

19May2023

CCI

intervention discontinuation but within the double-blind period will still be used within the analysis as estimated from the model using the GLIMMIX procedure.

For all secondary endpoints, a similar estimand to the one used for the primary analysis will be employed. That is, the estimand of interest will be based on overall mean monthly estimates across/within the double-blind period and will be based on all available data during that period (even if collected after study intervention discontinuation). Additionally, baseline values must also be available.

The primary and the key secondary estimands are described in Table E:

Table E: Estimands

Objective	Estimands
Primary	
To assess whether galcanezumab is superior to rimegepant in the prevention of migraine in participants with episodic migraine	
Treatment condition: Galcanezumab injections of 120 mg SC or rimegepant 75 mg ODT regardless of initiation of new preventive migraine medication, regardless the use of acute medication to treat a migraine headache and regardless of discontinuing treatment due to any reason (treatment policy strategy)
 
Population: Participants who meet IHS-ICHD-3 (2018) criteria for a diagnosis of migraine with or without aura with an episodic frequency of 4 to 14 migraine headache days per month and fulfils the inclusion and exclusion criteria of the study.
 
Variable (endpoint): The percentage of participants with $\geq 50\%$ reduction from baseline in monthly migraine headache days across the 3-month double-blind treatment period
 
Remaining intercurrent event handling: NA
 
Summary measure: Difference of the overall mean monthly 50% response rate across the 3-month double-blind treatment period between treatment

Document: **CCI**

Author: **PPD**

Version Number:

3.0

Version Date:

19May2023

CCI

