To compare galcanezumab	
Treatment condition: Galcanezumab injections of 120 mg SC or rimegepant 75 mg ODT,

Document: **CCI**Author: **PPD**Version Number: **3.0**Version Date: **19May2023**

Objective	Estimands
with rimegepant with respect to 75% response rate	
regardless of initiation of new preventive migraine medication, regardless the use of acute medication to treat an acute migraine attack and regardless of discontinuing treatment due to any reason (treatment policy strategy)

	
Population: Participants who meet IHS-ICHD-3 (2018) criteria for a diagnosis of migraine with or without aura with an episodic frequency of 4 to 14 migraine headache days per month and fulfills the inclusion and exclusion criteria of the study.

	
Variable (endpoint): The percentage of participants with $\geq 75\%$ reduction from baseline in monthly migraine headache days across the 3-month double-blind treatment period

	
Remaining intercurrent event handling: NA

	
Summary measure:

	
Difference of the overall mean monthly 75% response rate across the 3-month double-blind period between treatment groups

To compare galcanezumab with rimegepant with respect to monthly migraine headache days at each month	
Treatment condition: Galcanezumab injections of 120 mg SC or rimegepant 75 mg ODT, regardless of initiation of new preventive migraine medication, regardless the use of acute medication to treat an acute migraine attack and regardless of discontinuing treatment due to any reason (treatment policy strategy)

	
Population: Participants who meet IHS-ICHD-3 (2018) criteria for a diagnosis of migraine with or without aura with an episodic frequency of 4 to 14 migraine headache days per month and fulfills the inclusion and exclusion criteria of the study.

	
Variable (endpoint): The mean change from baseline in the number of monthly migraine headache days at:

Document: CCI

Author: PPD

Version Number: 3.0

Version Date: 19May2023

Objective	Estimands
	
 o Month 3 o Month 2 o Month 1
	
Remaining intercurrent event handling: NA

	
Summary measure: Difference of the mean change from baseline in the number of monthly migraine headache days at:
 
 o Month 3 o Month 2 o Month 1

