To compare galcanezumab with rimegepant with respect to 100% response rate	
Treatment condition: Galcanezumab injections of 120 mg SC or rimegepant 75 mg ODT, regardless of initiation of new preventive migraine medication, regardless the use of acute medication to treat an acute migraine attack and regardless of discontinuing treatment due to any reason (treatment policy strategy)
 
Population: Participants who meet IHS-ICHD-3 (2018) criteria for a diagnosis

Document: CCI

Author: PPD

Version Number: 3.0

Version Date: 19May2023

Objective	Estimands
	of migraine with or without aura with an episodic frequency of 4 to 14 migraine headache days per month and fulfils the inclusion and exclusion criteria of the study.
	Variable (endpoint): The percentage of participants with 100% reduction from baseline in monthly migraine headache days across the 3-month double-blind treatment period
	Remaining intercurrent event handling: NA
	Summary measure: Difference of the overall mean monthly 100% response rate across the 3-month double-blind period between treatment groups

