6.5. STATISTICAL TESTS

The primary objective is to demonstrate that galcanezumab is superior to rimegepant in reducing migraine headaches as measured by average monthly response rate across a 3-month period (in this case, the 3-month double-blind period). If one lets π_G and π_R = the true 3-month average monthly 50% response rates for galcanezumab and rimegepant respectively, *the null and alternative hypotheses are as follows:*

$$H_0: \pi_G \leq \pi_R \text{ against } H_a: \pi_G > \pi_R$$

The corresponding hypotheses for secondary objectives with response rate based estimands (for example, average monthly 75% response rate) are identical as those for the primary (with corresponding changes to the true response rate of interest).

For secondary objectives that are to demonstrate the superiority of galcanezumab over rimegepant as measured by continuous measures (for example, reduction from baseline in monthly migraine headache days), the null and alternative hypotheses would be of the form:

$$H_0: \mu_G \leq \mu_R \text{ against } H_a: \mu_G > \mu_R$$

Where μ_G and μ_R are the true mean reductions for galcanezumab and rimegepant, respectively.

Document: **CCI**

Author: **PPD**

Version Number:

3.0

Version Date:

19May2023

CCI

While all hypotheses given above are 1-sided, these hypotheses will operationally be evaluated via 2-sided tests.

The default significant level will be (5%); confidence intervals will be 95% (2-sided), unless otherwise specified in the description of the analyses.

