18.2.3. PRIMARY ANALYSIS OF PRIMARY EFFICACY VARIABLE(S)

The primary objective of this study is to assess whether galcanezumab is superior to rimegepant in the prevention of migraine in participants with episodic migraine. The primary estimand of interest is the overall mean monthly 50% response rate across the 3-month double-blind period attributable to the randomized treatment based on all available data as estimated from the model based on GLIMMIX-procedure. All available monthly migraine headache data will contribute to analysis as long as baseline monthly migraine headache day values are available. Any migraine headache day data collected after study intervention discontinuation but within the double-blind period will still be used within the analysis.

The primary efficacy analysis will be performed for the ITT. This endpoint (50% responder) is binary variable with repeated measures and will be analyzed using a GLIMMIX procedure as pseudo-likelihood-based mixed effects repeated measures analysis. The GLIMMIX procedure will include the fixed, categorical effects of treatment, month, and treatment-by-month interaction, as well as the continuous, fixed covariate of baseline monthly migraine headache days value. Binary distribution and logit link will be used.

An unstructured covariance structure will be used to model the within-participant errors (denoted by TYPE=CHOL in the RANDOM statement). The Newton-Raphson method with ridging will

Document: **CCI**

Author: **PPD**

Version Number:

3.0

Version Date:

19May2023

CCI

be used for nonlinear optimization (denoted by including NLOPTIONS TECH=NRRIDG). The Kenward-Roger (Kenward and Roger 1997) approximation will be used to estimate denominator degrees of freedom. If the model does not converge, the Fisher scoring algorithm will be utilized by the SCORING option in SAS.

If the model still fails to converge, the model will be fit using covariance matrices in the following order specified by a decreasing number of covariance parameters until convergence is met:

- Heterogeneous Toeplitz,
- Heterogeneous autoregressive,
- Toeplitz, and
- Autoregressive.

If necessary, both fitting algorithms will be used in the pre-specified order before proceeding to the next covariance structure in the sequence.

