For models where the unstructured covariance matrix is not utilized, the sandwich estimator (Diggle et al. 1994) will be used to estimate the standard errors of the fixed effects parameters. The sandwich estimator is utilized by the EMPIRICAL option in SAS. When the sandwich estimator is utilized, the Kenward-Roger approximation for denominator degrees of freedom cannot be used. Instead, the denominator degrees of freedom will be partitioned into between-subject and within-subject portions by the DDFM=BETWITHIN option in SAS.

For the repeated binary efficacy measure where the objective is to assess the proportion of patients with 50% response during the 3-month double-blind treatment phase, the endpoint for comparing galcanezumab with rimegepant will be estimated as the treatment main effect from the categorical MMRM analysis assessing the response rate across Months 1, Month 2 and Month 3.

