18.3.2. ANALYSIS OF SECONDARY EFFICACY VARIABLES

18.3.2.1. Analysis of Key Binary Secondary Efficacy Endpoints

Dichotomous outcomes will be analyzed using a the same GLIMMIX as pseudo- likelihood-based mixed effects repeated measures analysis used for the primary endpoint. The GLIMMIX procedure will include the fixed, categorical effects of treatment, month, and treatment-by-month interaction, as well as the continuous, fixed covariate of baseline for the variable of interest. Please refer to Section 18.2.3 for details.

For the repeated binary efficacy measure where the objective is to assess the proportion of patients with X% response during the 3-month double-blind treatment phase, the endpoint for comparing galcanezumab with rimegepant will be estimated as the treatment main effect from the categorical MMRM analysis assessing the average response rate across Months 1, Month 2 and Month 3.

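### The responder estimands and nulls are differences in 3-month average response rates, but the SAP estimates a logit-scale main effect and specifies no step that yields the rate difference or its confidence interval

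*SAP*

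**What the plan says.** The target is on the rate scale. Table E in SAP 2.4 gives the primary summary measure as "Difference of the overall mean monthly 50% response rate across the 3-month double-blind treatment period between treatment" groups. For the two key secondary responder endpoints it gives "Difference of the overall mean monthly 75% response rate across the 3-month double-blind period between treatment groups" and "Difference of the overall mean monthly 100% response rate across the 3-month double-blind period between treatment groups". SAP 6.5 writes the primary null in terms of "the true 3-month average monthly 50% response rates for galcanezumab and rimegepant respectively" and applies the same form to the other response rates. The sample size (SAP 3.1.1, Protocol 9.5) assumes a treatment difference of 12%.

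The estimator is on another scale. SAP 18.2.3 fits GLIMMIX with treatment, month, treatment-by-month and continuous baseline migraine headache days, and states "Binary distribution and logit link will be used". It says that the between-arm comparison "will be estimated as the treatment main effect from the categorical MMRM analysis". SAP 18.3.2.1 repeats this for 75% and 100% response: the comparison "will be estimated as the treatment main effect from the categorical MMRM analysis assessing the average response rate" over the three months.

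Two other statements bear on the point. SAP 18.2.3 says that the overall mean monthly rate is estimated from the model, without saying how. Protocol 9.3.1 promises 95% CIs for differences in LSMeans, which under a logit link are log odds ratios unless converted.

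**The concern.** With a treatment-by-month term, the treatment main effect under a logit link is the equally weighted mean of three monthly log odds ratios at a given baseline value. The estimand is the difference between two means of three probabilities. The mean of logits is not the logit of the mean, so these are different quantities and their nulls can differ.

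Two things are at stake. First, the trial's hypotheses, estimand and planning assumption are all in percentage points, yet the derivation of that difference and its CI is left open until after unblinding. Second, H03 and H09 are alpha-controlled. If the two arms' monthly profiles differ in shape, the main-effect test can reject more or less often than 2.5% one-sided when the average rates are equal.

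**Working it through.** **Inputs from the documents.** About 575 randomised 1:1, so 287.5 per arm; one-sided 0.025 (SAP 2.1); logit link with treatment-by-month; a 12-point planning difference. Monthly responder rates and within-person correlation are not given, because the planning details are withheld to preserve blinding. All rates, profiles and correlations below are assumptions.

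**The plan's own figure.** More than 85% power with up to 10% dropout (575 × 0.9 = 517.5 evaluable) cannot be confirmed without the withheld inputs. Taking 50% v 62% as an example, a single binary endpoint gives 78.7%. The mean of three monthly binaries with correlation 0.5 gives 92.2%. The stated figure is attainable and is not in question here.

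**Primary endpoint, size of the mismatch.** Assume rimegepant 42/50/58% and galcanezumab 58/62/66%.
- True difference: 62.0 − 50.0 = 12.0 points.
- Monthly log odds ratios: 0.646, 0.490, 0.341. Mean 0.492, odds ratio 1.64.
- Back-transforming each arm's mean logit: 62.1% − 50.0% = 12.1 points.
- With a baseline slope of up to −0.2 per day over 4 to 14 days, the odds ratio reaches about 1.70 and the back-transformed difference about 13.0 points.

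**Test level when the average rates are equal.** For monthly rates p_j in one arm:
- mean logit = (1/3) Σ ln[p_j/(1 − p_j)]
- s_j = 1/√[n p_j(1 − p_j)]; variance of the mean logit = (1/9) Σ_j Σ_k ρ_jk s_j s_k, with ρ_jj = 1 and ρ_jk = 0.5 otherwise
- one-sided rejection = 1 − Φ(1.96 − d/SE), where d is galcanezumab minus rimegepant

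Worked case for H03, galcanezumab flat 22% and rimegepant 14/22/30%:
- Rimegepant logits −1.815, −1.266, −0.847, mean −1.309; galcanezumab mean −1.266; d = 0.044.
- Variances 0.01351 and 0.01446; SE = √0.02797 = 0.167; d/SE = 0.26.
- Rejection = 1 − Φ(1.70) = 4.5%.

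| Endpoint | Galcanezumab | Rimegepant | d | One-sided rejection |
|---|---|---|---|---|
| 50% (H01) | flat 50% | 42/50/58% | 0.000 | 2.5% |
| 75% (H03) | same monthly rates in both arms | same | 0.000 | 2.5% |
| 75% (H03) | flat 22% | 18/22/26% | 0.010 | 2.9% |
| 75% (H03) | flat 22% | 14/22/30% | 0.044 | 4.5% |
| 75% (H03) | flat 22% | 10/22/34% | 0.110 | 9.3% |
| 75% (H03) | 14/22/30% | flat 22% | −0.044 | 1.3% |
| 100% (H09) | flat 10% | 6/10/14% | 0.057 | 4.3% |
| 100% (H09) | flat 10% | 4/9/17% | 0.162 | 9.8% |

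Moving the correlation between 0.3 and 0.7 changes the 4.5% only to 4.8% or 4.3%. The H09 rows ignore the gates before it.

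**Check by simulation.** A marginal logistic model with a baseline covariate and sandwich standard errors was run 4,000 times per scenario at 287 per arm. For flat 30% v 20/30/40%, the logit main effect rejects in 4.2% and the standardised rate difference in 2.3%. For flat 10% v 5/10/15%, the figures are 6.6% and 2.6%. For flat 50% v 42/50/58%, they are 2.4% and 2.5%.

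**Back-transforming the LSMean is not enough.** Monthly rates of 5/10/15% average 10.0%, but the inverse logit of their mean logit is 9.2%.

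**The case against.** A reader might infer that the rate difference will never be produced. The documents do not support that. SAP 18.2.3 says that the rate is estimated from the model, and SAP 8 places table content in output templates that are not part of the documents. What stands is narrower: no averaging, back-transformation, standardisation or standard error is specified.

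A reader might also infer that H01 is compromised, or that the trial carries a 9–10% error rate. Neither follows. The 50% test keeps its level in the cases checked. Inflation on H03 needs equal 3-month averages together with a flatter galcanezumab profile; with matching monthly rates the level holds, and with the profiles reversed the test is conservative. The 9.3% case requires rimegepant to be 12 points ahead at Month 3 (34% v 22%). The only hint of a rising rimegepant profile is the rationale for Amendment a in Protocol 10.8, which is superseded and concerns migraine days, not 75% or 100% response.

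Gatekeeping matters for H09. Under SAP 7.4 it is reached only after H01 to H08, including superiority on migraine days at Months 3, 2 and 1 (H04 to H06). That sits poorly with rimegepant well ahead on 100% response at Month 3. The H09 figures are therefore unconditional and overstate the practical risk. H03 follows only H01 and H02, so the error-rate argument rests mainly there.

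The last objection bears on the remedy. SAP 18.2.3 calls the model mixed effects, with TYPE=CHOL in the RANDOM statement, but also refers to within-participant errors. If random effects are fitted and simply set to zero when predicting, the 12.0-point difference above becomes about 14 to 19 points for an assumed random-intercept SD of 1 to 2. The calculations here use the marginal reading; rejection rates under a random-effects fit were not simulated.

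**Conclusion.** The mismatch between estimand and estimator is in the text and applies to all three responder endpoints. For the 50% endpoint it is a gap in the effect estimate and CI, not in the test. For H03 the level against the stated null depends on the shape of the monthly profiles, in either direction: between 1.3% and 9.3% one-sided over the assumed profiles, and close to nominal for mild divergence. H09 shares the defect but is partly protected by its gates. These sizes rest on assumed rates, correlation 0.5, 287.5 per arm and a marginal model. When d is not zero the departure grows with sample size, which the interim analysis may increase. The plan should be changed, though nothing here suggests that the primary conclusion would be wrong.

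**What to change.** In SAP 18.2.3 and 18.3.2.1:
- Define each arm's 3-month mean response rate as the average, over participants' baseline values and Months 1 to 3, of marginal predicted probabilities. These come from a residual-side (marginal) fit, or from a random-effects fit with the random effects integrated out. State which fit is intended.
- Report the between-arm difference with a delta-method or bootstrap 95% CI as the Table E estimate for 50%, 75% and 100% response.
- Base H01, H03 and H09 on that same contrast, so that p-value and interval agree.
- If the sample size is increased, use this contrast's z-statistic in the CHW combination that Protocol 9.3.2 and 9.3.3 require for the primary and key secondary endpoints.
- Keep the odds ratio as supportive.

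The cost is SAP wording and modest extra programming, with no new data.

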18.2.4. SENSITIVITY ANALYSIS OF PRIMARY EFFICACY VARIABLE(S)

The following sensitivity analyses are of the primary efficacy variable are planned:

- I) To consider the case where to discard the data of the participants that discontinue treatment and may have different expectations regarding efficacy of the two treatments such as the onset of effect given the different dosing and mode of administration of the comparators. For such analyses, the data after whichever of the following is sooner will be discarded: the date of the last injection+30 days or the

Document:

CCI

Author:

PPD

Version Number:

3.0

Version Date:

19May2023

date of the last oral administration +1 day.

- II) To consider participants that withdraw for lack of efficacy or tolerability, or participants that switch preventive treatment as no responders (composite strategy).
- III) To consider a migraine headache day when the participant takes acute medication regardless of the headache does not meet the criteria of migraine. This analysis will consider if a participant uses an acute medication (triptans or ergot derivatives) – as reported in the CRF (CM_AHM), regardless of whether a headache was reported. For this analysis baseline and post-baseline ‘migraine headache days’ need to be defined using the reporting of medications in CM_AHM CRF. Input from clinical will be used to help identify the classes of acute medication used.
- IV) To assess the robustness of the primary analysis conclusions to deviations from missing at random (MAR) assumption. The approach for these analyses is to vary the assumptions of missing data for the primary analysis in a systematic way. Basically, the method will be to predict the missing outcomes and then add values ($\Delta_{120}, \Delta_{75}$) to the predictions in the Galcanezumab 120 mg and rimegepant 75 mg treatment groups respectively, regardless of the reason the data are missing. This approach is consistent with the sensitivity approach suggested in Permutt (2015). This procedure will be repeated multiple times for different values of ($\Delta_{120}, \Delta_{75}$) using the following steps:
 - 1) Predict the missing outcomes for each treatment via multiple imputation based on observed primary endpoint and baseline values. Such imputation will be carried out using a Markov Chain Monte Carlo method with a Jeffreys prior via SAS® PROC MI. Thirty (30) such imputations will be created.
 - 2) Add the corresponding Δ value (i.e. $\Delta_{120}, \Delta_{75}$) to the imputed values based on the patient treatment group.
 - 3) Conduct the primary analysis separately for each of the 30 imputations.
 - 4) Combine the results of these analyses using Rubin’s combining rules, as implemented in SAS® PROC MI ANALYZE.

The above steps will be repeated multiple times for different values of ($\Delta_{120}, \Delta_{75}$) with Δ_{75} ranging from 0 to twice the absolute value of the mean value seen for rimegepant in the primary analysis, Δ_{120} ranging from Δ_{75} to $\Delta_{75} + \text{absolute value of the biggest mean treatment difference seen within the primary analysis}$. For example, if the overall mean change from

Document: **CCI**

Author: **PPD**

Version Number:

3.0

Version Date:

19May2023

CCI

baseline for rimegepant is -3.6 and the maximum overall treatment difference is -1.5, then Δ_{75} would range from 0 to 7.2 and Δ_{120} would range from Δ_{75} to $\Delta_{75} + 1.5$.

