## **9.5. Sample Size Determination**

The study will screen an estimated 1150 potential study participants to ensure a minimum of approximately 575 randomized participants. Based on the assumption of treatment difference of 12%, the minimum sample size of approximately 575 provides more than 85% power at a two-sided significance level of 5% and a dropout rate of no more than 10%, with the opportunity to increase the final sample size at the interim analysis if indicated to maintain a well-powered study. To preserve blinding, details of the sample size and power calculations are omitted from this protocol and are provided to the ERB in a separate document. If the interim is not performed, then the trial will enroll to a sample size as specified in the ERB document.

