To compare galcanezumab with rimegepant with respect to monthly migraine headache days	
Treatment condition: Galcanezumab injections of 120 mg SC or rimegepant 75 mg ODT, regardless of initiation of new preventive migraine medication, regardless the use of acute medication to treat an acute migraine attack and regardless of discontinuing treatment due to any reason (treatment policy strategy)
 
Population: Participants who meet IHS-ICHD-3 (2018) criteria for a diagnosis of migraine with or without aura with an episodic frequency of 4 to 14 migraine headache days per month and fulfills the inclusion and exclusion criteria of the study.
 
Variable (endpoint): The overall mean change from baseline in the number of monthly migraine headache days across the 3-month double-blind treatment period
 
Remaining intercurrent event handling: To assess the robustness of the primary analysis conclusions to

Document: CCI

Author: PPD

Version Number: 3.0

Version Date: 19May2023

Objective	Estimands
	
deviations from missing at random (MAR) assumption, this analysis will vary the assumptions of missing data for the primary analysis in a systematic way.

	
Summary measure: Difference of the overall mean change from baseline in the number of monthly migraine headache days across the 3-month double-blind treatment period

Key Secondary	
To compare galcanezumab with rimegepant with respect to monthly migraine headache days	
Treatment condition: Galcanezumab injections of 120 mg SC or rimegepant 75 mg ODT, regardless of initiation of new preventive migraine medication, regardless the use of acute medication to treat an acute migraine attack and regardless of discontinuing treatment due to any reason (treatment policy strategy)

	
Population: Participants who meet IHS-ICHD-3 (2018) criteria for a diagnosis of migraine with or without aura with an episodic frequency of 4 to 14 migraine headache days per month and fulfils the inclusion and exclusion criteria of the study.

	
Variable (endpoint): The overall mean change from baseline in the number of monthly migraine headache days across the 3-month double-blind treatment period

	
Remaining intercurrent event handling: NA

	
Summary measure: Difference of the overall mean change from baseline in the number of monthly migraine headache days across the 3-month double-blind treatment period

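### With similar missingness in the two arms, the delta grid in SAP 18.2.4 item IV goes no further than equal outcomes among missing participants, so it is not a full tipping-point check

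*SAP*

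**What the plan says.** SAP 18.2.4 lists four sensitivity analyses. Item IV is the one whose stated purpose is "To assess the robustness of the primary analysis conclusions to deviations from missing at random (MAR) assumption". It works as follows.

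- "Predict the missing outcomes for each treatment via multiple imputation based on observed primary endpoint and baseline values", with 30 imputations.
- A constant is added to every imputed value, delta-120 for galcanezumab and delta-75 for rimegepant, "regardless of the reason the data are missing".
- Each completed data set is analysed, and the results are combined by Rubin's rules.

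Delta-75 takes values "ranging from 0 to twice the absolute value of the mean value seen for rimegepant in the primary analysis". Delta-120 runs from delta-75 up to delta-75 plus the "absolute value of the biggest mean treatment difference seen within the primary analysis". The SAP gives an example in which the mean change from "baseline for rimegepant is -3.6 and the maximum overall treatment difference is -1.5". No search beyond these limits is described.

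SAP 2.4, Table E, gives this analysis (Primary Sensitivity 4) a continuous variable: "The overall mean change from baseline in the number of monthly migraine headache days across the 3-month double-blind treatment period". On that scale a positive delta makes a participant worse. The primary endpoint itself is the binary 50% response (SAP 18.2.1 and 18.2.3).

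**The concern.** The trial tests whether galcanezumab is superior. The departure from MAR that most directly threatens that claim is one in which participants with missing data (called leavers below) do worse on galcanezumab than on rimegepant. Capping the extra galcanezumab penalty at the observed benefit stops the grid about where that region begins.

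The gap lies in how the deltas are paired, not in how large they are. The grid admits galcanezumab leavers who end up worse than at baseline, provided rimegepant leavers are about equally bad. It excludes a milder case in which galcanezumab leavers merely return to baseline while rimegepant leavers follow the MAR prediction.

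The plan gives some reason to expect different behaviour in the two arms. Item I of the same section recognises that people who stop may view the efficacy of the two treatments differently, because dosing and mode of administration differ. Protocol 7.2 has participants leave the study before starting another effective agent, so exits for lack of effect can become missing data. Item II does not fill the gap, because it applies one non-responder rule to both arms.

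At stake is the meaning of a favourable item IV. Readers will take it as evidence of robustness to departures from MAR, although the asymmetric adverse departures were not examined.

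**Working it through.** **1. The SAP's own figures.** Delta-75 maximum = 2 × |-3.6| = 7.2. Maximum of delta-120 minus delta-75 = |-1.5| = 1.5. Both reproduce. The implied galcanezumab mean is -3.6 - 1.5 = -5.1.

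**2. What the grid says about leavers.** Leaver mean = MAR-imputed mean + delta, taking the imputed mean as equal to the arm mean.

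| delta-75 | delta-120 | Galcanezumab leavers | Rimegepant leavers | On grid? |
|---|---|---|---|---|
| 0 | 0 | -5.1 | -3.6 | yes |
| 0 | 1.5 | -3.6 | -3.6 | yes, at the cap |
| 3.6 | 5.1 | 0 | 0 | yes, at the cap |
| 7.2 | 8.7 | 3.6 | 3.6 | yes, far corner |
| 0 | 5.1 | 0 | -3.6 | no |

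Every point at the cap gives equality.

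**3. Effect on the estimate.** With missing shares fG and fR, difference = -1.5 + fG × delta-120 - fR × delta-75. If both shares are 10% (assumed; Protocol 9.5 allows dropout of up to 10%), any point at the cap gives -1.5 + 0.10 × 1.5 = -1.35. The omitted point (0, 5.1) gives -1.5 + 0.10 × 5.1 = -0.99.

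**4. Effect on the test.** Approximate variance per arm = [SD² + f(1 - f) × delta²] / [n(1 - f)], with n = 575/2 = 287.5. This treats each participant as contributing one value. At f = 0.10 the denominator is 258.75.

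The stated power of more than 85% at two-sided 5% implies an expected z of about 1.96 + 1.04 = 3.0 at the design effect. Setting the MAR z to 3.0 with a 1.5-day difference makes the standard error 0.50, so SD² = 0.25 × 258.75 / 2 = 32.34 (SD about 5.7). The z values below are in absolute value.

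- Far corner (7.2, 8.7): variance = (64.69 + 0.09 × 75.69 + 0.09 × 51.84) / 258.75 = 0.294; SE 0.543; z = 1.35 / 0.543 = 2.49. This is the lowest on the grid.
- Omitted point (0, 5.1): variance = (64.69 + 0.09 × 26.01) / 258.75 = 0.259; SE 0.509; z = 0.99 / 0.509 = 1.95.

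**5. Other SDs.** The documents give no SD, so it is varied. The 1.5-day difference and 10% missing per arm are kept.

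| SD | MAR z | Lowest z on grid | z at (0, 5.1) | delta-120 at which significance is lost (delta-75 = 0) |
|---|---|---|---|---|
| 3 | 5.69 | 4.00 | 0.99/0.280 = 3.53 | 8.9 |
| 4 | 4.27 | 3.29 | 0.99/0.364 = 2.72 | 7.6 |
| 5 | 3.41 | 2.77 | 0.99/0.450 = 2.20 | 6.2 |

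At delta-75 = 0 the grid stops at delta-120 = 1.5, which is about 17% (1.5/8.9) to 24% (1.5/6.2) of the way to the tipping point.

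**6. Where the grid does bite.** At 10% missing per arm and SD 4, variance inflation lets it overturn MAR results with p between about 0.012 and 0.05. The lower limit is 0.006 at SD 3 and 0.016 at SD 5. With 15% missing on galcanezumab and 5% on rimegepant, the far corner gives -1.5 + 0.15 × 8.7 - 0.05 × 7.2 = -0.555 and |z| = 1.34 at SD 4. At 12% against 8% it gives -1.03 and |z| = 2.50.

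**7. Responder scale.** Take the 12-point design effect, 10% missing per arm, an assumed rimegepant rate of 40% to 50%, and an assumed between-month correlation of 0.5 to 1.0. Equal leaver outcomes leave 0.9 × 12 = 10.8 points (z about 2.6 to 3.2). Galcanezumab leavers as non-responders with rimegepant leavers at MAR leaves 0.9 × 52 - 40 = 6.8 points or 0.9 × 62 - 50 = 5.8 points (z about 1.4 to 2.0).

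**The case against.** The grid is not lenient in every respect. It penalises galcanezumab at least as much as rimegepant at every point, and it reaches leavers 3.6 days worse than baseline in both arms. The SAP never calls it a tipping-point analysis. Both arms are active and blinded by double dummy. Participants who stop treatment should stay in the study and their later data are used, so the missing share may be well below 10%. All of this stands, and it limits how much the gap matters.

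A reader might go further than the documents allow in four ways.

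- **That the grid cannot threaten the superiority claim.** It can: step 6 shows borderline results, and results with clearly more galcanezumab missingness, losing significance.
- **That galcanezumab leavers can never come out worse on the grid.** This is exact only if imputed leaver means equal the arm means. Imputation uses observed outcomes, so if galcanezumab leavers were already poorer responders, the cap passes equality. The word *biggest* might also be read as the largest monthly difference, although the example refers to an overall one. Small reversals are therefore possible.
- **That the SAP's example result would fail in the omitted case.** With a 1.5-day difference and SD 3 to 5, the point (0, 5.1) stays significant. The z of 1.95 needs a MAR z near 3.0, which for 1.5 days means an SD of about 5.7.
- **That tying the cap to the estimate is itself the fault.** It lets the grid run to about equality whatever the effect size. The weakness is that it stops there.

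**Conclusion.** The point holds in a limited form. With similar missingness and imputed means near the arm means, the only analysis aimed at departures from MAR takes equal leaver outcomes as its harshest contrast and omits those in which galcanezumab leavers do worse.

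The omission can decide the reading of a result of about the strength the trial is powered for: with a MAR z of 3.0, z stays at or above about 2.5 on the grid and is about 1.95 at the omitted point. It makes no difference to a very strong result, such as a MAR z of 4.27. These figures rest on assumed values for the missing share, its split between arms and the SD, and on an approximate variance formula. This is a supporting analysis; the primary test and its error control are not affected.

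**What to change.** Amend SAP 18.2.4 item IV before unblinding, since limits chosen afterwards would weaken the check.

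1. Let delta-75 and delta-120 vary independently, and drop the cap at the observed difference.
2. At each delta-75, starting at 0, raise delta-120 until two-sided p exceeds 0.05.
3. Report that boundary, the mean outcome it implies for leavers in each arm, the missing share per arm, and a judgement of clinical plausibility.
4. State how deltas in headache days carry over to the binary primary endpoint, for example whether shifted counts are converted to 50% response before the primary model is fitted. Added directly to a response rate, a positive delta would improve the outcome.

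The cost is a few sentences in the SAP and more runs of code that is already planned. The downside is that a tipping point will be on record and may look less favourable than a statement that the result survived the grid.
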